### Infusion Temporary Interruptions

Study drug infusion temporarily interrupted as recorded on the “Study Treatment Administration Details” page of the eCRF will be used for analysis. Number of participants with at least one study drug temporary interruption, reason for study drug temporary interruption (adverse event or other), as well as a categorization of the number of study drug temporary interruptions (1 / 2 /  $\geq 3$ ) will be summarized.

### Infusion Rate Reductions

Infusion rate reductions as recorded on the “Study Treatment Administration Details” eCRF page will be used for analysis. Number of participants with at least one infusion rate reduction, reason for infusion rate reductions (adverse event or other), as well as a categorization of the number of infusion rate reductions (1 / 2 /  $\geq 3$ ) will be summarized.

## 14 Efficacy Analyses

*Analysis Sets: ITT*

### 14.1 Best Overall Response according to RECIST 1.1 as adjudicated by IRC (Primary endpoint)

Analysis (Analysis Population)	Derivation	Statistical Analysis Methods	Missing data handling
Primary endpoint: confirmed Objective Response (OR)			
Primary analysis (ITT)	Confirmed Objective Response Rate (ORR) according to RECIST 1.1 as adjudicated by the IRC is defined as the number of participants having a confirmed objective response assessment of Complete Response (CR) or Partial Response (PR) (at least two determinations of CR/PR at least 4 weeks apart and before progression), out of the total number of participants.	ORR will be provided with a two-sided 95% Confidence Interval (CI) using the Clopper-Pearson method (exact CI for a binomial proportion as computed by default by the FREQ procedure using the EXACT option).  Exact binomial test (1 sample) against the null hypothesis for the ORR will be calculated to determine whether the null hypothesis of an ORR $\leq 10\%$ can be rejected.	Participants with missing post-baseline data are considered as having no objective response

### Best overall response (BOR)

Best overall response will be assessed based on the tumor response at different evaluation timepoints from the first study intervention until the first documented disease progression for RECIST criterion. Only tumor assessments performed before the start of any further anticancer treatment will be considered in the assessment of BOR. Clinical deterioration will not be considered as documented disease progression.

BOR can be defined as confirmed or unconfirmed, both definitions are provided below.

### Confirmed best overall response (cBOR)

cBOR according to RECIST 1.1 as adjudicated by IRC will be assessed according to the following rules:

- CR = at least two determinations of CR at least 4 weeks apart and before progression  
Note: It is reasonable to consider CR-NE-CR or CR-PR-CR as CR as long as the second CR is more than 28 days away from the first timepoint.
- PR = at least two determinations of PR at least 4 weeks apart and before progression (and not qualifying for a CR)  
Note: It is reasonable to consider PR-NE-PR or PR-SD-PR as PR as long as the second PR is more than 28 days away from the first timepoint
- SD = at least one SD assessment (or better)  $\geq$  6 weeks after first date of study intervention and before progression (and not qualifying for CR or PR)
- Non-CR/Non-PD= at least one Non-CR/Non-PD assessment  $\geq$  6 weeks after first date of study intervention and before progression with no measurable disease and does not meet criteria of CR

Note: As tumor lesions are evaluated by the IRC, it may happen that the independent reviewer disagrees with the Investigator and does not assess any tumors as “measurable” at screening. However, as per inclusion criteria, measurable disease must be confirmed by IRC at inclusion, so such case is not expected to occur. But in case of Non-CR/Non-PD, the overall response is rated as “non-CR/non-PD” (if no “CR” or “PD” are previously reported) by the IRC. Non-CR/Non-PD is specific to IRC assessment (it does not apply for Investigator assessment)

- PD = progression  $\leq$  16 weeks after first date of study intervention (and not qualifying for CR, PR or SD)
- ND = at least one ND assessment

Note: Overall response is rated as “No Disease” (ND) when the IRC is not able to identify any disease at baseline (target or non-target lesions). However, as per inclusion criteria, measurable disease must be confirmed by IRC at inclusion, so such case is not expected to occur. ND is specific to IRC assessment (it does not apply for Investigator assessment)

- NE = all assessments are NE or participant has a missing (or not evaluable) baseline tumor assessment and/or no (or not evaluable) tumor assessments on-treatment, or participant does not complete any of the following response above

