### Unconfirmed best Overall Response (uBOR)

uBOR according to RECIST 1.1 as adjudicated by IRC will be assessed according to the following rules:

- CR = at least one determination of CR

- PR = at least one determination of PR (and does not meet criteria of CR)
- SD = at least one SD assessment  $\geq$  6 weeks after start date and before progression (and does not meet criteria of CR or PR)
- Non-CR/Non-PD = at least one Non-CR/Non-PD assessment  $\geq$  6 weeks after start date and before progression with no measurable disease (and does not meet criteria of CR)

Note: As tumor lesions are evaluated by the IRC, it may happen that the independent reviewer disagrees with the Investigator and does not assess any tumors as “measurable” at screening. However, as per inclusion criteria, measurable disease must be confirmed by IRC at inclusion, so such case is not expected to occur. But in case of Non-CR/Non-PD, the overall response is rated as “non-CR/non-PD” (if no “CR” or “PD” are previously reported) by the IRC. Non-CR/Non-PD is specific to IRC assessment (it does not apply for Investigator assessment)

- PD = progression  $\leq 16$  weeks after first date of study intervention (and does not meet criteria of CR, PR, SD or Non-CR/Non-PD)
- ND = at least one ND assessment

Note: Overall response is rated as “No Disease” (ND) when the IRC is not able to identify any disease at baseline (target or non-target lesions). However, as per inclusion criteria, measurable disease must be confirmed by IRC at inclusion, so such case is not expected to occur. ND is specific to IRC assessment (it does not apply for Investigator assessment)

- NE = all assessments are NE or participant has a missing (or not evaluable) baseline tumor assessment and/or no (or not evaluable) tumor assessments on-treatment, or participant does not complete any of the following response above

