### **Objective Response Rate (ORR)**

The Objective Response Rate (ORR) is defined as the number of participants having an OR assessment of Complete Response (CR) or Partial Response (PR), out of the total number of participants.

Confirmed ORR will be determined as the proportion of participants with a confirmed OR of PR or CR (having at least two determinations of CR/PR at least 4 weeks apart and before progression).

The confirmed ORR according to RECIST 1.1 as assessed by the IRC is the primary endpoint of the study.

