### **Disease Control Rate (DCR)**

Disease Control Rate (DCR) is defined as the proportion of participants with BOR according to evaluation criteria of CR, PR, or SD out of the total number of participants.

Separate tables will be provided for confirmed and unconfirmed BOR. Each one will provide the number and percentage of participants with cBOR (respectively uBOR) of CR, PR, SD, Non-CR/Non-PD, PD, ND and NE as well as the ORR and the DCR. The ORR and DCR will be provided with a two-sided 95% CI using the Clopper-Pearson method (exact CI for a binomial

proportion as computed by default by the FREQ procedure using the EXACT option). Exact binomial test (1 sample) against the null hypothesis for the ORR will be calculated for confirmed BOR to determine whether the null hypothesis of an ORR  $\leq 10\%$  can be rejected.

The individual percentage of change in the sum of diameter since baseline will be displayed over time on a spider plot, together with the first occurrence of new lesion and the participant off treatment. The change in the sum of diameters between baseline and the best post-baseline assessment (i.e. minimum change since baseline) will be displayed on a waterfall graph. Note the sum of diameters includes all target lesions (longest diameter for non-nodal lesions and short axis for nodal target lesions)

The best percent change in sum of target lesion diameters will also be presented in a waterfall plot with confirmed BOR per IRC and investigator, PD-L1 in tumor cells and immune cells, **CCI**, **CCI** and **CCI** status.

For spider plots and waterfall plots, the percent change from baseline in the sum of diameters will be displayed for valid timepoint assessments, only. For the purpose of this analysis, a valid timepoint assessment is defined as a complete assessment of all target lesions reported at baseline. Further, split and coalesced lesions have to be taken into account appropriately to determine if a timepoint assessment is valid to derive the percent change from baseline in sum of diameters. All sum of diameters should be used, including the ones beyond first PD (for waterfall plot, the best post-baseline sum of diameters will be used even if occurring beyond PD). For waterfall plot, the percent change from baseline to 8-weeks assessment, as well as the percent change from baseline to the best post-baseline sum of diameters will be displayed for each participant.

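### SAP 14.1: one PR plus one CR counts as a confirmed response for ORR but is labelled SD for confirmed BOR, so the CR and PR rows can fall short of the ORR in the same table

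*SAP*

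**What the plan says.** **Confirmed ORR.** The primary-endpoint table in SAP 14.1 and the Objective Response Rate paragraph both pool the two response categories. A confirmed responder is a participant "having at least two determinations of CR/PR at least 4 weeks apart and before progression".

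**Confirmed BOR.** The cBOR rules in the same section do not pool. CR needs two CRs. The next category reads "PR = at least two determinations of PR at least 4 weeks apart and before progression (and not qualifying for a CR". Whoever is left with at least one adequate assessment from week 6 on goes to the category that begins "SD = at least one SD assessment (or better". The attached notes deal with some interrupted sequences, for instance "It is reasonable to consider CR-NE-CR or CR-PR-CR as CR", and with PR-NE-PR and PR-SD-PR. Every sequence in those notes contains two assessments of the same response category.

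**Unconfirmed BOR.** Here "CR = at least one determination of CR" is sufficient.

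**Where the labels appear.** The confirmed table lists the number of participants with a cBOR "of CR, PR, SD, Non-CR/Non-PD, PD, ND and NE as well as the ORR and the DCR". The best change in target lesions is also "presented in a waterfall plot with confirmed BOR per IRC and investigator". SAP 14.1.1 repeats cBOR and ORR by subgroup, and SAP 14.2 repeats the analysis for the Investigator read and cross-tabulates the two reads.

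**The concern.** The two rules are meant to describe the same responders, but they treat one PR plus one CR differently. Such a participant satisfies the ORR rule. The participant has neither two CRs nor two PRs, so the SD rule, which accepts SD or anything better, takes over. The SD rule contains that extension and the PR rule does not, and this is where the gap arises.

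The consequences are for presentation and consistency:

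- In the confirmed-BOR table, the CR and PR counts can add to less than the ORR. Protocol 9.4.1.1 defines objective response as the sum of CR and PR.
- The same person appears as a confirmed responder in the swimmer graph (SAP 14.5), as SD in the waterfall plot and subgroup cBOR tables, and as CR in the unconfirmed table.
- In the IRC-versus-Investigator comparison, an IRC read of PR-CR (SD) against an Investigator read of PR-PR (PR) shows as a category disagreement, although both readers saw a confirmed response. If both read PR-CR, the result is SD against SD and counts as concordant.
- SAP 16.4.1 and 16.4.2 define a responder in the ADA and nAb listings as confirmed CR or PR without saying which rule applies.

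**Working it through.** **Design figures, for reference (Protocol 9.2).** N = 141, null ORR 10%, assumed ORR 18%, one-sided alpha 0.025, success at 22 or more responders.

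- P(X ≥ 22 | 141, 0.10) = 0.0239.
- P(X ≥ 22 | 141, 0.18) = 0.8007, which reproduces the stated 80%.
- Clopper-Pearson interval for 22/141: 10.04% to 22.66%, which matches the stated 10% to 22.7%.

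**Timing conditions.** Scans are every 8 weeks in the first 12 months (Protocol 8.1.1). Two scheduled scans are therefore normally more than 4 weeks apart, and the first falls after week 6, so neither the 4-week nor the 6-week condition usually excludes a PR-CR pair.

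**The rules applied as written, stopping at first PD.**

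| Sequence | ORR responder | cBOR | uBOR | cBOR if PR rule says PR or better |
|---|---|---|---|---|
| PR-CR-PD | yes | SD | CR | PR |
| SD-PR-CR-PD | yes | SD | CR | PR |
| PR-SD-CR-PD | yes | SD | CR | PR |
| PR-PR-CR | yes | PR | CR | PR |
| PR-CR-PR | yes | PR | CR | PR |
| PR-CR-CR | yes | CR | CR | CR |
| CR-PR-CR | yes | CR | CR | CR |
| PR-PR-PD | yes | PR | PR | PR |
| PR-SD-PD | no | SD | PR | SD |

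**All sequences over three scans.** With states CR, PR, SD, NE and PD at weeks 8, 16 and 24, cut at the first PD, there are 4³ + 4² + 4 + 1 = 85 distinct sequences.

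- 14 of the 85 meet the ORR rule but have neither cBOR CR nor cBOR PR. Each has exactly one PR and one CR, and each is labelled SD.
- The count can be checked by hand. There are 2 orders of PR and CR × 3 positions for the third scan × 2 states (SD or NE) = 12, plus the 2 orders followed by PD = 14.
- None conflicts in the other direction: two CRs or two PRs at least 4 weeks apart always satisfy the pooled rule. The CR and PR rows can only fall short of the ORR.
- Accepting PR or better in the PR rule moves all 14 from SD to PR and changes no other label.

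**Size per affected participant.**

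- Overall: 1/141 = 0.7 percentage points; 2/141 = 1.4; 3/141 = 2.1.
- BTC subtype at the minimum of 30 in Protocol 4.1: 1/30 = 3.3 percentage points.

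**The case against.** **The ORR wording could mean CR or PR respectively.** Two CRs would then confirm a CR and two PRs a PR, and the rules would agree. The SAP never says this. SAP 14.5 points the other way: it treats a confirmed response as two objective responses and dates it from the first CR or PR. On the alternative reading, a participant who improves from PR to CR and then progresses would not be a responder at all. The primary endpoint would then depend on a rule that is nowhere stated.

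**Other text ties ORR to cBOR.** The heading of SAP 14.1 calls best overall response the primary endpoint, the exact test is described as calculated for confirmed BOR, and Protocol 9.4.1.1 sums CR and PR. This shows that the two were meant to agree. It does not redefine ORR, which the same section states explicitly in pooled form. It does show what a programmer could get wrong. If 22 responders included one PR-CR pair and the test were run on the cBOR rows, 21/141 would give p = 0.0419 instead of 0.0239. If 2%, 5% or 10% of responders had only a mixed pair (an assumed range), power from the cBOR rows would be 76.9%, 71.5% or 61.1% instead of 80.1%. That is a programming hazard and does not make the test as written wrong.

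**RECIST 1.1 or the IRC charter may settle the case.** Neither is in the documents. The point is therefore limited to the SAP derivation, which sets out its own rules for assigning cBOR.

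**It is rare and visible.** This stands. At an 18% ORR about 0.18 × 141 = 25 responders are expected, and mixed pairs would be a subset. Some pairs still in response at the primary cut-off may gain a third qualifying scan by the 15-month analysis; pairs that end in progression will not. A shortfall would be apparent in the table, but the SAP would give no rule for resolving it.

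**Conclusion.** The concern holds as a minor defect. Followed literally, SAP 14.1 labels a participant with exactly one PR and one CR as SD in the confirmed-BOR outputs while counting the same participant as a confirmed responder in the ORR. The error runs in one direction only.

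The conclusion rests on the pooled reading of the ORR rule, on the PR and CR being at least 4 weeks apart, and on both preceding progression and any new anticancer therapy. The number of participants affected is not given and cannot be derived from the documents.

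The primary ORR test as written, its threshold and its power do not change. DOR and DRR follow the pooled definition, and DCR counts SD, so none of these is affected.

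**What to change.** Reword the cBOR PR category along these lines: *two or more assessments of PR or better (PR or CR), separated by 4 weeks or longer and preceding progression, when the CR rule is not met.*

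Add one sentence stating that confirmed ORR is the proportion of participants with cBOR of CR or PR. It should cover the IRC analysis (14.1), the Investigator analysis (14.2) and the responder definition in the ADA and nAb listings (16.4.1 and 16.4.2).

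The cost is one amended rule, one added sentence and a one-line change to the derivation. Sample size, alpha, success threshold, power and trial conduct stay as they are.

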### Unconfirmed best Overall Response (uBOR)

uBOR according to RECIST 1.1 as adjudicated by IRC will be assessed according to the following rules:

- CR = at least one determination of CR

- PR = at least one determination of PR (and does not meet criteria of CR)
- SD = at least one SD assessment  $\geq$  6 weeks after start date and before progression (and does not meet criteria of CR or PR)
- Non-CR/Non-PD = at least one Non-CR/Non-PD assessment  $\geq$  6 weeks after start date and before progression with no measurable disease (and does not meet criteria of CR)

Note: As tumor lesions are evaluated by the IRC, it may happen that the independent reviewer disagrees with the Investigator and does not assess any tumors as “measurable” at screening. However, as per inclusion criteria, measurable disease must be confirmed by IRC at inclusion, so such case is not expected to occur. But in case of Non-CR/Non-PD, the overall response is rated as “non-CR/non-PD” (if no “CR” or “PD” are previously reported) by the IRC. Non-CR/Non-PD is specific to IRC assessment (it does not apply for Investigator assessment)

- PD = progression  $\leq 16$  weeks after first date of study intervention (and does not meet criteria of CR, PR, SD or Non-CR/Non-PD)
- ND = at least one ND assessment

Note: Overall response is rated as “No Disease” (ND) when the IRC is not able to identify any disease at baseline (target or non-target lesions). However, as per inclusion criteria, measurable disease must be confirmed by IRC at inclusion, so such case is not expected to occur. ND is specific to IRC assessment (it does not apply for Investigator assessment)

- NE = all assessments are NE or participant has a missing (or not evaluable) baseline tumor assessment and/or no (or not evaluable) tumor assessments on-treatment, or participant does not complete any of the following response above

### **Objective Response Rate (ORR)**

The Objective Response Rate (ORR) is defined as the number of participants having an OR assessment of Complete Response (CR) or Partial Response (PR), out of the total number of participants.

Confirmed ORR will be determined as the proportion of participants with a confirmed OR of PR or CR (having at least two determinations of CR/PR at least 4 weeks apart and before progression).

The confirmed ORR according to RECIST 1.1 as assessed by the IRC is the primary endpoint of the study.

### **Disease Control Rate (DCR)**

Disease Control Rate (DCR) is defined as the proportion of participants with BOR according to evaluation criteria of CR, PR, or SD out of the total number of participants.

Separate tables will be provided for confirmed and unconfirmed BOR. Each one will provide the number and percentage of participants with cBOR (respectively uBOR) of CR, PR, SD, Non-CR/Non-PD, PD, ND and NE as well as the ORR and the DCR. The ORR and DCR will be provided with a two-sided 95% CI using the Clopper-Pearson method (exact CI for a binomial

proportion as computed by default by the FREQ procedure using the EXACT option). Exact binomial test (1 sample) against the null hypothesis for the ORR will be calculated for confirmed BOR to determine whether the null hypothesis of an ORR  $\leq 10\%$  can be rejected.

The individual percentage of change in the sum of diameter since baseline will be displayed over time on a spider plot, together with the first occurrence of new lesion and the participant off treatment. The change in the sum of diameters between baseline and the best post-baseline assessment (i.e. minimum change since baseline) will be displayed on a waterfall graph. Note the sum of diameters includes all target lesions (longest diameter for non-nodal lesions and short axis for nodal target lesions)

The best percent change in sum of target lesion diameters will also be presented in a waterfall plot with confirmed BOR per IRC and investigator, PD-L1 in tumor cells and immune cells, **CCI**, **CCI** and **CCI** status.

For spider plots and waterfall plots, the percent change from baseline in the sum of diameters will be displayed for valid timepoint assessments, only. For the purpose of this analysis, a valid timepoint assessment is defined as a complete assessment of all target lesions reported at baseline. Further, split and coalesced lesions have to be taken into account appropriately to determine if a timepoint assessment is valid to derive the percent change from baseline in sum of diameters. All sum of diameters should be used, including the ones beyond first PD (for waterfall plot, the best post-baseline sum of diameters will be used even if occurring beyond PD). For waterfall plot, the percent change from baseline to 8-weeks assessment, as well as the percent change from baseline to the best post-baseline sum of diameters will be displayed for each participant.

Listing of tumor assessment will be provided with the following information: participant identifier, age, sex, race, date of start of subsequent anticancer therapy, date of death when death occurs, unconfirmed and confirmed BOR, visit, date(s) of imaging, description of target lesions (size, site, type, method, response), non-target lesions (status, site, type, method, response), and new lesions (site, type, method), sum of lesion diameters, percent change in target lesions from baseline, percent change in target lesions from nadir and overall response of participant. Note that response of target and non-target lesions and change from nadir is not applicable at baseline.

In addition, a summary table of the reasons for non-evaluable confirmed BOR will be provided, the following reasons will be detailed:

- No baseline assessment (if applicable)
- No post-baseline assessments due to death within 8 weeks after the start of study treatment
- No post-baseline assessments due to other reasons
- All post-baseline assessments have overall response 'Non-evaluable'
- New anticancer therapy started before first evaluable post-baseline assessment
- SD of insufficient duration (<6 weeks after the start of study treatment)

Note: Special cases where BOR is NE due to both early SD and late PD will be classified into this category

- Non-CR/Non-PD of insufficient duration (<6 weeks after the start of study treatment) (if required by the data)
- No evaluable tumor assessment >16 weeks followed by PD (i.e. tumor assessment of PD was >16 weeks after start of study treatment and there was no evaluable tumor assessment in between)
- No IRC review and Not determined categories may also be added if applicable

A listing of reasons for non-evaluable confirmed BOR will also be created including: participant identifier, age, sex, race, date of first and last dose, date(s) of imaging, overall response and the reason for confirmed BOR non-evaluable.

